### 3.5.3 Pharmacokinetic Parameter

For subjects with serial samples collected (pre-dose and at 0.5, 1, 2, 3, 4, and 6 hour post-dose after the first CCX140-B dose on Day 1 and on Day 15),  $C_{max}$ ,  $T_{max}$ , and  $AUC_{0-6}$  will be determined based on individual CCX140 plasma concentration data.  $AUC_{0-12}$  or  $AUC_{0-24}$  will be determined for Day 15 assuming pre-dose level being the same as the concentration at the end of the dosing interval.

Parameters	Description
$C_{\max}$	Maximum drug concentration after the first dose; observed directly from the data. If not unique, then the first maximum concentration is used
$T_{\max}$	Time to $C_{\max}$
$AUC_{0-6}$	Area under the concentration-time curve (AUC) from time 0 to 6 hours post-dose. For 6 hours post-dose sample, the corresponding observed concentrations will be used for AUC calculation if the difference of the actual time point is <5% from the nominal time point; otherwise, the concentration at the nominal 6-hour time point will be predicted and then used for the AUC calculation.
$AUC_{0-12}$	AUC from time 0 to 12 hours post-dose on Day 15 only following 10 or 15 mg BID dosing (Groups C and D). The concentration at 12-hour time point will be assumed to be the same as the pre-dose level.
$AUC_{0-24}$	AUC from time 0 to 24 hours post-dose on Day 15 only following 5 mg QD dosing (Group B). The concentration at 24-hour time point will be assumed to be the same as the pre-dose level.

PK parameter calculations will be based on all seven continuous time points from Day 1 and Day 15 (including Time 0). The PK parameters of those subjects with less than seven continuous time points are listed as NA.

Plasma PK parameters will be calculated by standard non-compartmental analysis. The actual collection times will be used for PK parameter calculation. The linear trapezoidal rule method (equivalent to the Linear Trapezoidal Linear Interpolation in WinNonlin® Professional) will be used in the computation of AUCs.

PK parameters will be listed and summarized by treatment descriptively.

The relationship between PK parameters and renal function based on eGFR, UPCR and UACR change of UPCR or UACR from baseline, and serum albumin will be evaluated through an exploratory analysis and summarized in a separate report.

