#### 2.3.4 *Pharmacokinetic Endpoints*

Concentrations of CCX140 will be determined in plasma from 4.0-mL blood samples collected in K2EDTA tubes according to Table 1. The following parameters will be determined, where possible:

- Cmax Maximum plasma concentration
- Tmax Time of maximum plasma concentration
- AUC0-6 Area under the plasma concentration-time curve from Time 0 to Hour 6 on Day 1 and Day 15
- Cmin Trough level plasma concentrations at post-Day 1 visits

On Days 1 and 15, samples will be taken at pre-dose, 0.5, 1, 2, 3, 4, and 6 hours after dosing. The blood samples collected on the other relevant study days need to be collected prior to taking the CCX140-B/ placebo dose.

The relationship between PK and serum albumin and between PK and UPCR may be explored, where possible.

Total plasma concentrations of CCX140 will be determined using validated analytical methods. These plasma samples may also be used to measure other markers associated with FSGS.

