## 3.5 Pharmacokinetic and Pharmacodynamic Marker Analysis

### 3.5.1 Data Assembly

The concentration data of CCX140 as reported by the respective bioanalytical group will be used without rounding for all analysis.

Subjects with major protocol deviation such as PK deviation or compliance issues may be excluded from the PK analyses (i.e. descriptive statistics) upon agreement with the Sponsor on case by case basis but all data will be listed. Values that are excluded from the analysis will be footnoted appropriately.

The following general rules should apply for handling missing data or concentration below the lower limit of quantification (BLQ) on Day 1:

- All BLQs will be set to “0” for Day 1 visit.
- If the BLQ occurs between 2 quantifiable drug concentrations within a full PK profile for Day 1 visit, the BLQ is excluded from all PK assessments.
- Missing pre-dose concentrations on Day 1 will be set as “0” and included in PK evaluation
- Missing post-dose values on Day 1 will not be imputed and will be excluded from PK evaluation
- Values that are excluded from the analysis will be documented appropriately.
- Pre-dose values on Day 1 that are greater than 5% of  $C_{max}$  will be documented. A sensitivity analysis (with inclusion and exclusion of the subjects with the pre-dose concentration  $>5\%$  of  $C_{max}$ ) will be presented and documented in the study report.

The following general rules should apply for handling missing or BLQ data on Day 15:

- If the BLQ occurs between 2 quantifiable drug concentrations within a full PK profile for Day 15 visit, the BLQ is excluded from all PK assessments.
- Missing pre-dose concentrations on Day 15 will be not imputed and excluded from PK evaluation. In case of missing pre-dose concentration on Day 15, AUCs on Day 15 will not be calculated for this subject.
- Missing post-dose values on Day 15 will not be imputed and will be excluded from PK evaluation
- Values that are excluded from the analysis will be documented appropriately.

The sample time of the pre-dose samples on Day 1 and Day 15 will be uniformly considered as

time “0”.

For the trough concentration for post-Day 1 visits and at 2 days, 7 days and 14 days after the last dose of study drug, all missing or BLQ concentration will not be imputed and will be excluded from the descriptive summary.

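### The SAP's all-or-nothing seven-sample rule for PK parameters conflicts with its own Day 15 and late pre-dose rules, and discards parameters that can be computed

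*SAP*

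**What the plan says.** SAP 2.3.4 sets seven samples per profile day: "On Days 1 and 15, samples will be taken at pre-dose, 0.5, 1, 2, 3, 4, and 6 hours after dosing".

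SAP 3.5.3 then sets a completeness condition. "PK parameter calculations will be based on all seven continuous time points from Day 1 and Day 15 (including Time 0"), and "The PK parameters of those subjects with less than seven continuous time points are listed as NA". The same section takes Cmax as the highest measured concentration and computes AUC by the linear trapezoid at actual collection times.

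SAP 3.5.1 works sample by sample:
- Day 1 pre-dose missing: "Missing pre-dose concentrations on Day 1 will be set as" zero, and kept in the evaluation.
- Day 1 post-dose missing: "Missing post-dose values on Day 1 will not be imputed and will be excluded from PK evaluation". Day 15 has the same rule: "Missing post-dose values on Day 15 will not be imputed and will be excluded from PK evaluation".
- Day 15 pre-dose missing: "In case of missing pre-dose concentration on Day 15, AUCs on Day 15 will not be calculated for this subject".
- A value below the limit of quantification (BLQ) lying between two measurable ones: "If the BLQ occurs between 2 quantifiable drug concentrations within a full PK profile for Day 1 visit, the BLQ is excluded from all PK" work. Day 15 has a matching rule.
- Pre-dose sample drawn after dosing, either day: it is treated as a post-dose value and used in the parameter calculation.

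Protocol 8.3 and SAP 2.3.4 say only that parameters are determined where possible. SAP section 6 does not list a seven-sample condition among the changes from the protocol.

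**The concern.** Two programmers could build different PK tables from the same data, because the SAP does not say whether 3.5.1 or 3.5.3 governs when a sample is missing. If 3.5.3 governs, one lost tube removes Cmax, Tmax and every AUC for that profile, including parameters that do not depend on the lost sample.

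The PK profile is a secondary objective with 10 subjects planned per dose. Protocol 2.4 states exposure limits as AUC0-24 and Cmax, and the Day 15 parameters are the planned measures closest to those limits. The exploratory comparison of PK parameters with eGFR, UPCR and serum albumin would draw on the same reduced set.

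**Working it through.** The plan gives no figure on this point to reproduce. The check is a comparison of rules, followed by an illustration of size.

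**Step 1: the rules side by side**

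| Event | SAP 3.5.1 | SAP 3.5.3 | Compatible? |
|---|---|---|---|
| Day 15 pre-dose missing | AUCs withheld; nothing said against Cmax, Tmax | All parameters NA | No. If 3.5.3 governs, the AUC-only rule has no function |
| Pre-dose drawn after dosing | Used in parameter calculation | Time 0 required, otherwise NA | No, most clearly on Day 15, where no Time 0 value is imputed |
| One post-dose sample missing | That value left out | Whole profile NA | Yes, if applied in sequence, but computable results are lost |
| One embedded BLQ | That value left out | Six points remain, so NA | Same as the row above |
| Day 1 pre-dose missing | Set to zero and kept | Zero can serve as Time 0 | Yes; no conflict |

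**Step 2: how many profiles the rule could void**

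Inputs: seven samples per day (SAP 2.3.4) and 10 subjects per arm (SAP 2.2.1). The per-sample loss rate p is an assumption, 2% to 5%, independent between samples. Day 1 has six vulnerable samples, because the pre-dose value is imputed. Day 15 has seven.

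- Day 1: 1 − (1 − p)^6. At 2%, 1 − 0.98^6 = 11.4%. At 3%, 16.7%. At 5%, 1 − 0.95^6 = 26.5%.
- Day 15: 1 − (1 − p)^7. At 2%, 1 − 0.98^7 = 13.2%. At 3%, 19.2%. At 5%, 1 − 0.95^7 = 30.2%.
- Day 15 profiles left per arm of 10: 10 × 0.868 = 8.7 at 2% and 10 × 0.698 = 7.0 at 5%.
- If the wording of 3.5.3 means both days must be complete (13 vulnerable samples): 1 − (1 − p)^13 = 23% at 2% and 49% at 5%.
- If losses cluster, fewer profiles are hit. In the extreme, where a whole profile is lost or none of it, the share is p itself, 2% to 5%, and no rule could recover those profiles.

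For scale, the 90% confidence half-width for a mean is t(0.95, n − 1)/√n standard deviations: 0.58 at n = 10 and 0.73 at n = 7. The SAP plans only descriptive PK summaries, so this shows lost precision and is not a planned interval.

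**Step 3: whether the discarded values are usable**

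Dropping one interior sample changes a trapezoidal AUC by half the distance between its neighbours times the gap between the dropped value and the straight line joining them. The widest case is the 4-hour sample: (6 − 3)/2 = 1.5 h. Protocol 6.4 projects a steady-state trough of about 5500 and a peak of about 6500 ng/mL at 15 mg twice daily, without proteinuria. If all values lie in that band, the change is at most 1.5 × 1000 = 1500 ng·h/mL against an AUC0-6 of at least 6 × 5500 = 33,000, so below 5% (1500/33,000 = 4.5%).

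On an invented smooth profile in that band (5500, 5900, 6250, 6500, 6420, 6320, 6100 ng/mL), the largest AUC change was 0.44%, with the 2-hour peak dropped. Cmax changed only in that case, from 6500 to 6420 (80/6500 = 1.2%). This covers steady state only; Day 1 starts from zero and could be more sensitive.

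**The case against.** The strongest reply is that the two sections work at different levels. SAP 3.5.1 prepares the data and 3.5.3 decides when a parameter may be reported, so they can be applied in order. That stands for a missing post-dose sample: 3.5.1 never promises that parameters will be computed from the remaining points. It also stands for a missing Day 1 pre-dose value. A reader might infer that the sections cannot be followed together at all, or that losing any one of the seven samples voids the profile. The documents do not support either reading.

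Even for the Day 15 pre-dose sample, the survival of Cmax and Tmax is implied by what 3.5.1 leaves unsaid. But a sentence that withholds only the AUCs is redundant if everything is NA anyway, and the late pre-dose rule says outright that the value enters the parameter calculation. Those two conflicts remain.

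A complete-profile requirement is also a defensible caution for some parameters: Cmax and Tmax are unreliable when a sample near the peak is missing, and AUC0-6 needs a 6-hour value. That supports conditions for each parameter, not one condition for all of them.

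The consequence is limited. Concentrations are still listed, plotted and summarised, trough summaries are untouched, and the PK–renal analysis is exploratory. An embedded BLQ also looks unlikely on Day 15 in the top-dose arm, given the projected concentrations.

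**Conclusion.** The point holds as an internal inconsistency and an avoidable loss of data. The blanket NA rule conflicts with 3.5.1 on the missing Day 15 pre-dose sample and on the pre-dose sample drawn after dosing. Elsewhere it is compatible but wasteful, because it removes parameters that the SAP's own methods can compute.

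The size is conditional. The losses of about 11% to 27% of Day 1 profiles and 13% to 30% of Day 15 profiles rest on an assumed 2% to 5% loss per sample, independence, and a rule applied separately to each day. A reader might take them as expected losses. The documents give no missing rate, and samples from one clinic visit may well be lost together, which lowers the figures. Nothing here bears on the primary efficacy analysis.

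**What to change.** Replace the seven-point sentence in SAP 3.5.3 with a rule stated per day and per parameter, and align 3.5.1 with it:
- AUC0-6: compute from the available samples when there is a Time 0 value (observed, or imputed under 3.5.1) and a 6-hour value.
- Day 15 AUC0-12 and AUC0-24: require the observed pre-dose value as well, since it stands in for the end-of-interval concentration.
- Cmax and Tmax: report from the observed samples, and flag profiles that lack a sample near the peak.
- State how a pre-dose sample drawn after dosing is handled for each parameter on each day.
- Footnote every reduced profile and show the complete-profile summary as a sensitivity check.

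Under the same assumed 2% to 5% loss, Day 1 AUC0-6 would be lost only with the 6-hour sample (2% to 5%). Day 15 AUCs would be lost with either end sample: 1 − 0.98² = 4.0% to 1 − 0.95² = 9.8%.

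The cost is SAP wording and some programming, best settled before unblinding. A few parameters will rest on sparser profiles, and Cmax may be slightly underestimated in the flagged subjects.

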## 3.6 Safety Assessment

Safety analyses will be performed for the Safety Population. All safety assessments will be based on actual treatments received by participants.

### 3.6.1 Adverse Events (AEs)

An overview of AEs will be provided including counts and percentages of subjects (and event counts) with the following:

- Any TEAEs (overall and by maximum severity)
- Any study drug related TEAEs (overall and by maximum severity)
- Any treatment-emergent serious AEs (TESEAEs)
- Any TEAEs leading to discontinuation of study drug
- Any AEs leading to death

Counts and percentages of subjects (and event counts) will also be presented by system organ class (SOC) and preferred term (PT) using the Medical Dictionary for Regulatory Activities (MedDRA) Version 20.1 any TEAEs and TESEAEs for 3 Safety Populations separately. Counts and percentages of subjects (and event counts) will also be presented by PT in decreasing frequency for any TEAEs and TESEAEs for 3 Safety Populations (see 3.2.4 for definitions) separately.

TEAEs for the Safety Population in each period are defined as an event with a start date on or after the first study drug treatment in each period and up to the final observation in each period. Treatment periods for analysis of adverse event are defined in Section 3.2.4. TEAEs for the All CCX140-B Treated Population are defined as an event with a start date on or after the first dose of CCX140-B up to the final observation.

Listings will be presented specifically for SAEs and TEAEs leading to discontinuation of study drug.

The severity of AEs was assessed by the investigator using the following protocol definitions:

- Mild (Grade 1): no limitation of usual activities
- Moderate (Grade 2): some limitation of usual activities
- Severe (Grade 3): inability to carry out usual activities
- Life-threatening (Grade 4): an immediate risk of death
- Death (Grade 5)

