9.3.6. Safety Analyses

All clinical safety and tolerability data will be listed by treatment group and by subject, and will be summarized by treatment group and visit.

Treatment-emergent adverse events (TEAE) will be summarized for each treatment group by MedDRA System Organ Class (SOC) and preferred term (PT), by relatedness and maximum severity. Treatment-emergent serious adverse events (TESAE) and TEAE leading to study withdrawal will be separately listed and may be summarized if warranted by the subject incidences.

Vital signs and laboratory test results, and their changes from baseline will be summarized by treatment group and visit. Abnormal laboratory values will be flagged in the data listing. Shift tables will be generated by study visit.

Individual ECG findings and change from baseline in ECG findings will be listed by treatment group, subject, and study visit, and summarized by treatment group and visit.

Findings from physical examinations will be listed.

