#### Notations for Treatment Groups

Period A: initial 12-week blinded treatment period, Day 1 –Week12

Period B: open-label treatment period plus 4 Weeks of Follow-up, Week 12 to End of Study (EOS)

We have defined 3 Safety Populations for this study:

1. The Safety Population in Period A (Safety\_A) is defined as all subjects who received at least one dose of study drug in Period A.
2. The Safety Population in Period B (Safety\_B) is defined as all subjects who received at least one dose of study drug in Period B.
3. The All CCX140-B Treated Population is defined as all subjects received at least one dose of CCX140-B in the study.

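### Adverse-event tables for the All CCX140-B population and Period B have no person-time denominator, so they cannot be read fairly against 12 weeks of placebo or across unequal follow-up

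*SAP*

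**What the plan says.** SAP 3.6.1 sets out two kinds of adverse-event table. For the overview: "An overview of AEs will be provided including counts and percentages of subjects (and event counts) with the following". For the tables by system organ class and preferred term, the measure is again subjects, percentages and events, for example "Counts and percentages of subjects (and event counts) will also be presented by PT in decreasing frequency for any TEAEs". These tables are produced separately for three safety populations.

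The windows come from SAP 3.2.4 and 3.6.1:

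- Safety_A: "Period A: initial 12-week blinded treatment period, Day 1" to Week 12.
- Safety_B: "Period B: open-label treatment period plus 4 Weeks of Follow-up, Week 12 to End of Study (EOS").
- All CCX140-B: "The All CCX140-B Treated Population is defined as all subjects received at least one dose of CCX140-B in the study".

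For the two period populations, an event is treatment-emergent if it has a "start date on or after the first study drug treatment in each period and up to the final observation in each period". For All CCX140-B it is "an event with a start date on or after the first dose of CCX140-B up to the final observation".

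SAP 3.3.7 summarises duration of exposure for the double-blind period, the open-label period and both together, but does not connect it to adverse events. Protocol 9.3.6 says that safety data "will be summarized by treatment group and visit". Neither document plans an exposure-adjusted rate or a time-to-event analysis of adverse events.

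**The concern.** The chance that a subject has at least one event grows with the time watched, and so does the number of events. A percentage or an event count can therefore be compared between columns only if the columns cover similar time.

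The All CCX140-B window starts at the first active dose. That is Day 1 for a subject randomised to active, and the start of open label for a subject randomised to placebo. One table therefore holds subjects with very different observation times. The only placebo data cover the 12-week blinded period in about 10 subjects, so they are the natural reference for anything seen in the longer windows.

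Safety and tolerability is a primary objective. With no true difference in risk, the longer windows will show more subjects with events and more events. That can be taken for toxicity, or dismissed as longer follow-up when it is real. The planned tables do not let a reader tell which. Period B also combines 12 weeks on drug with 4 weeks off drug, so an on-drug signal can be diluted, or mixed with events that follow withdrawal.

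**Working it through.** **Inputs.** Protocol synopsis: 4 weeks screening, 12 blinded, 12 open label, 4 follow-up, about 32 in total. SAP 2.2.1: 10 subjects per arm, so 10 placebo and 30 active. Protocol 8.5: the last visit is Week 16 for subjects who do not enter the extension. No event rate or hazard is given, so the 12-week incidence p is an assumption, varied from 5% to 70%.

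**The plan's own figure.** 4 + 12 + 12 + 4 = 32 weeks, as stated. After first dose: 84 + 84 + 28 = 196 days = 28 weeks.

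**Windows.**

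- Period A: 12 weeks, every arm.
- Period B: 12 + 4 = 16 weeks, every arm (Day 85 to Day 198 is 113 days, or 16.1 weeks).
- All CCX140-B, randomised to active and completing open label: 12 + 12 + 4 = 28 weeks.
- All CCX140-B, former placebo completing open label: 12 + 4 = 16 weeks.
- All CCX140-B, randomised to active and stopping at Week 12: 12 + 4 = 16 weeks.

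If all 40 enter and complete open label, mean follow-up in All CCX140-B is (10 × 16 + 30 × 28)/40 = 25 weeks.

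**Effect on percentages.** Assume a constant hazard, equal in all arms and periods, and no dropout. Then incidence by week w is 1 − (1 − p)^(w/12). For p = 30%:

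- 16 weeks: 1 − 0.7^(16/12) = 37.8%
- 28 weeks: 1 − 0.7^(28/12) = 56.5%
- pooled: (10 × 37.8 + 30 × 56.5)/40 = 51.8%

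| 12 weeks | 16 weeks | 28 weeks | All CCX140-B pooled |
|---|---|---|---|
| 5% | 6.6% | 11.3% | 10.1% |
| 10% | 13.1% | 21.8% | 19.6% |
| 20% | 25.7% | 40.6% | 36.9% |
| 30% | 37.8% | 56.5% | 51.8% |
| 50% | 60.3% | 80.2% | 75.2% |
| 70% | 79.9% | 94.0% | 90.5% |

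From the 5% row to the 70% row, the ratio of percentages falls from 1.32 to 1.14 (16 v 12 weeks), from 1.71 to 1.18 (28 v 16 weeks), and from 2.02 to 1.29 (pooled v 12-week placebo).

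**Effect on event counts.** Expected events per subject are proportional to time: 16/12 = 1.33, 28/16 = 1.75, 28/12 = 2.33.

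**Dependence on open-label entry.** If nobody entered, All CCX140-B would be the 30 active subjects at 16 weeks each, and the 30% event would show as 37.8%. If everybody enters, it shows as 51.8%. Partial entry lies between.

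**What a rate would show.** For p = 30% the hazard is −ln(0.7)/12 = 0.0297 per week. First events per 100 patient-weeks at risk are then 2.97 in expectation for every window, so the artificial differences vanish.

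**The case against.** The strongest reply is that the comparison that matters most is intact. The three populations are tabulated separately. Within Period A every randomised arm has the same planned 12 weeks, and within Period B every arm has the same planned 16, so apart from early discontinuation crude percentages are comparable there. This stands. A reader might infer from the absence of person-time that the arm comparisons are distorted throughout, including the placebo-controlled one. The SAP's window definitions do not support that.

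A reader might also infer that the All CCX140-B table will show former placebo and active arms side by side, with a spurious gap of about 9 to 20 points (28 v 16 weeks, for 12-week incidences of 10% to 50%). SAP 3.6.1 does not specify the columns, and SAP 3.6 bases safety on treatment actually received. Protocol 9.3.6 refers to treatment groups but not to this population, which only the SAP defines. The gap also needs the active subjects to enter and complete open label, and entry is conditional (Protocol 5.4). So the gap is a possibility, not a planned display. If a single pooled column is used, the problem becomes mixed follow-up, read against 12 weeks of placebo.

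It is also fair that the plan is not limited to percentages: event counts, maximum severity, listings and an exposure summary are all there. But event counts grow with time too, and dosing duration is not the observation time for adverse events.

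Finally, this is a 40-subject exploratory study with no planned test on adverse events. For 37.8% v 56.5% with 10 per arm, the 90% half-width is 1.645 × √(0.378 × 0.622/10 + 0.565 × 0.435/10), about 36 points. Chance would swamp much of the distortion, and rates by preferred term would be unstable. That limits how far the rates can be pressed, but is no reason to leave out the denominator.

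**Conclusion.** The point holds for two uses of the tables: the All CCX140-B Treated Population itself, and any reading of that population or of Period B against the 12-week placebo data. It does not extend to arm comparisons within Period A or within Period B.

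For a 30% event, equal risk would appear as 37.8% (Period B) or about 52% (All CCX140-B pooled) against 30% on placebo. These figures are illustrative. They rest on an assumed incidence, a constant and equal hazard that continues through the off-drug weeks, no dropout and full open-label entry. The unequal windows do not rest on those assumptions, since they follow from the SAP's definitions and the visit schedule.

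This is a worthwhile, inexpensive improvement to the safety reporting, not a flaw in the randomised safety comparison.

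**What to change.** In SAP 3.6.1:

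1. For All CCX140-B and Safety_B, keep the crude counts and percentages. Add subjects with a first event per 100 patient-weeks at risk, and events per 100 patient-weeks, to the overview and the SOC/PT tables. Show patient-weeks in each column.
2. Define time at risk: for first events, from the first relevant dose to the first event or the final observation; for event counts, to the final observation.
3. State the columns of the All CCX140-B tables (pooled, by randomised arm, or both).
4. In Period B, show on-drug events separately from those in the 4-week follow-up.
5. Keep the Period A crude percentages as the main randomised safety comparison.

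The cost is some SAP wording and a few table columns. The dose and event dates are already needed for SAP 3.3.7 and for the treatment-emergent definitions.

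The rates have limits that a footnote should give. They assume a roughly constant hazard, and are unstable for rare preferred terms with about 10 subjects per arm. They do not remove the other differences between periods: blinding, dose, and selection into the extension.

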- The date and time of the last dose of CCX140-B or placebo prior to collection of the PK sample will be recorded
- Blood samples will be collected before dose administration for serum chemistry (including coagulation panel and lipids), hematology, serum pregnancy test (in women of childbearing potential), PK (time 0 only), plasma MCP-1, and PD (including lymphocyte subset) measurements; record the time of blood collection
- **Process the first morning void urine sample collection for quantitative urinalysis, UPCR, UACR, Cystatin C, Urine MCP-1, MCP-1/creatinine ratio and urine PD assessments**
- **Process the 24-hour urine sample collection for quantitative urinalysis, UPCR, UACR, Cystatin C, Urine MCP-1, MCP-1/creatinine ratio, urine PD assessment, and urine protein excretion/day**
- Subjects will be asked to complete the SF-36 v2 and EQ-5D-5L.
- The ACTG Brief Peripheral Screening Tool will be administered
- If the subject has not yet taken the morning dose of CCX140-B/placebo for this day, the subject will be asked to take the dose
- Drug accountability and reconciliation with subject completed diaries

- All study drug medication containers must be returned and drug usage must be reconciled against the completed diaries since continuing subjects will be given new drug supply of active study medication for open label dosing.
- Any changes in concomitant medication use will be recorded
- Any adverse events will be recorded
- **Assessment of continuing eligibility requirements:**
 - **has not withdrawn consent for the study**
 - **has no new infections that in the judgment of the investigator would preclude addition of a new immunosuppressive or immunomodulatory treatment**
 - **has had no requirement for the addition of new immunosuppressive treatment during the prior 12 weeks and no anticipated requirement during the next 12 weeks**
- **Provide the subject with the kit for collection of the first morning void**
- After all study procedures have been completed, **discontinuing subjects** will be reminded to:
 - **come to the study center at 2 days, 7 days and 14 days after the last dose for PK elimination and**
 - **come to the study center for the Week 16 follow-up visit**
- **Continuing subjects will be reminded to:**
 - Complete their diary each day immediately after each dose
 - Come to the study center for the Week 13 study visit, before taking the dose of **study drug**

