### 2.3.6 Safety Endpoints

#### 2.3.6.1 Adverse Events

Safety endpoints related to adverse events include subject incidence of treatment-emergent adverse events (TEAE), adverse events leading to study withdrawal, and serious adverse events. An adverse event will be considered treatment-emergent if the start date of the event is on or after the date of administration of the first dose of study medication.

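### An adverse event dated on the Week 12 visit day falls in both treatment periods when open-label dosing starts that day, and for placebo subjects it becomes a CCX140-B event even if found before the first active dose

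*SAP*

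**What the plan says.** SAP 3.2.4 defines "Period A: initial 12-week blinded treatment period, Day 1 –Week12" and "Period B: open-label treatment period plus 4 Weeks of Follow-up, Week 12 to End of Study (EOS"). Week 12 is therefore both the end of one period and the start of the next.

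Under SAP 3.6.1, a period's TEAEs are events with a "start date on or after the first study drug treatment in each period and up to the final observation in each period". For All CCX140-B Treated the condition is a "start date on or after the first dose of CCX140-B up to the final observation". SAP 2.3.6.1 makes clear that the comparison is between dates: an event counts if the "start date of the event is on or after the date of administration of the first dose of study medication". Results for the three safety populations are presented separately, and SAP 3.6 bases safety assessments on the treatment actually received.

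At the Week 12 visit (Protocol 7.7), "Blood samples will be collected before dose administration for serum chemistry (including coagulation panel and lipids), hematology, serum pregnancy test" and other tests. The ECG, neuropathy tool and adverse event recording take place at the same visit, and continuing subjects receive their open-label supply. In the Time and Events Table the open-label dosing row begins in the Day 85 / Week 12 column.

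**The concern.** The last day of Period A and the first day of Period B can be the same calendar date. The rule includes both ends and looks only at dates, so it cannot separate an event found before the first open-label dose from one that began after it.

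The consequence is clearest in the placebo arm. Protocol 8.2.3 allows an abnormal laboratory finding to be an adverse event. If the pre-dose Week 12 sample from a placebo subject shows one, and its onset is dated to that day, the SAP reports it as emerging on CCX140-B. That runs against the principle in the same protocol section that events before study medication begins are pre-treatment. Active arms are affected in a milder way: an event that arose on 5 mg once daily also enters the period planned at 15 mg twice daily.

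At stake is attribution in the tables that serve the primary safety objective. Protocol 2.4 considers red cell changes likely to carry over to humans, and the Week 12 bloods include the haematology used to detect them.

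**Working it through.** The plan gives no figure for this point. The check applies the date rule to the calendar.

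**Inputs**
- Blinded dosing lasts 84 consecutive days (Protocol 4; SAP 2.2.1), so it covers Days 1 to 84.
- Open-label dosing lasts a further 84 days, and drug stops as of Day 169 (SAP 2.2.1). 84 + 84 = 168, so open-label dosing covers Days 85 to 168, with a nominal first dose on Day 85.
- The Week 12 visit is on Day 85, with a window of 3 days either side (Protocol 7.7), so it can fall on Days 82 to 88.
- Period A's final observation is taken to be the Week 12 visit, because SAP 3.2.4 ends the period there.

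**Rule as written**
- In A if: first blinded dose date ≤ event date ≤ Week 12 visit date.
- In B if: first open-label dose date ≤ event date ≤ end of study.

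**Result for a visit on Day 85**

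| First open-label dose | Event on Day 84 | Event on Day 85 | Event on Day 86 |
|---|---|---|---|
| Day 85 (visit day) | A | A and B | B |
| Day 86 (next day) | A | A | B |
| None | A | A | neither |

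With the visit moved to Day 82 or Day 88 and the first open-label dose on the visit day, the overlap is again exactly one day, the visit date. With a next-day first dose there is no overlap.

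**Placebo subject, first open-label dose on the visit day, event dated that day**
- Safety_A: counted, on placebo.
- Safety_B: counted, on CCX140-B.
- All CCX140-B Treated: counted, because the event date equals the date of the first CCX140-B dose.

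The pre-dose timing of the blood sample plays no part in any of these three tests.

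**Illustration of scale, assuming one such subject.** If all 40 subjects receive CCX140-B, the All CCX140-B Treated percentage moves by 1/40 = 2.5 points. If all 10 placebo subjects continue and Safety_B is shown by randomised arm, that column moves by 1/10 = 10 points. Both are hypothetical, since the documents give no event rate for that day.

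**Search for a tie-break.** Neither document has a clock-time or same-day rule for adverse events. SAP 3.3.7 places Day 85 in the first 12 weeks, but only for exposure intervals. SAP 3.1.2 assigns Days 72 to 88 to Week 12, but only for efficacy visits.

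**The case against.** The strongest reply is that the same-date premise is not certain. Protocol 7.7 refers to the visit-day morning dose as CCX140-B or placebo, the exposure intervals put Day 85 with the blinded period, and SAP 3.5.1 describes the open-label phase as running from Week 13. A subject whose first open-label dose is on the next day has no overlap. This stands as a condition. It does not remove the point: the 84-day count and the dosing row both put the first open-label dose on the visit day, and a first dose that evening still shares the date.

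A reader might infer that events are counted twice. The documents do not support that. The three populations are reported separately and no table adds Safety_A to Safety_B.

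A reader might also expect events to cluster at Week 12 because so much is measured then. The rule uses the start date, not the date of discovery, so a symptom reported at Week 12 that began earlier falls in Period A. The exposed events are mainly findings dated to that day's tests.

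Those findings also remain visible elsewhere. Laboratory values are summarised by visit with shift tables (SAP 3.6.2), ECG abnormalities are listed by visit (3.6.4), and the neuropathy tool is summarised by visit (3.6.6). This limits the harm but does not correct the TEAE tables.

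Finally, sending every same-day event to Period A would be anti-conservative for a drug with a haematological signal of concern, and would sit badly with SAP 2.3.6.1. That objection stands, and the fix below respects it. Detailed programming specifications are kept in a separate document (SAP 7) and might hold a tie-break, but an attribution rule belongs in the SAP.

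**Conclusion.** The point holds in a limited form. As written, SAP 3.2.4 and 3.6.1 place an event dated on the Week 12 visit day in both periods whenever the first open-label dose is taken that day, as the schedule plans. For placebo subjects the event also enters All CCX140-B Treated, whether or not it preceded active drug. This is a stated rule that gives a wrong attribution, not merely an absent detail.

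The size is one calendar day per continuing subject, with an unknown number of events. The conclusion rests on the Week 12 visit being Period A's final observation and on a visit-day first dose.

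It would go too far to say that the primary safety objective is materially biased, or to treat the 10-point shift as an expected effect. The 10-point figure needs one such event, all 10 placebo subjects continuing, and Safety_B shown by randomised arm. SAP 3.2.4 analyses by randomised group unless the wrong drug was taken, while SAP 3.6 uses actual treatment, so that layout is not settled.

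**What to change.** Add a single-period rule to SAP 3.6.1:

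- Each adverse event is assigned to one period only.
- An event on the date of the first open-label dose that is documented as before that dose belongs to Period A only. Examples are a finding from the pre-dose Week 12 blood sample or an event with an earlier recorded time. For placebo subjects it is not a TEAE in All CCX140-B Treated.
- A same-day event documented as after the dose belongs to Period B.
- A same-day event whose order relative to the dose is unknown belongs to Period B, in line with the date-of-first-dose rule in SAP 2.3.6.1, and is flagged in the listing.

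An event moved to Period A remains treatment-emergent under SAP 2.3.6.1, because it follows the first blinded dose. Only its period and treatment attribution change.

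The cost is one SAP paragraph and a listing flag. No new data field is required: Protocol 7.7 already has the Week 12 blood collection time recorded and the sample drawn before dosing. The downside is that a few untimed events that began before the dose may still be credited to CCX140-B and would leave the Safety_A table.
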